 - Hematologic intolerance: Patients with grade 3 or 4 toxicity (absolute neutrophil count [ANC] or platelets) while on therapy that is recurrent after dose reduction to the lowest doses recommended by manufacturer
6. Eastern Cooperative Oncology Group (ECOG) performance status (PS) of 0, 1, or 2
7. Adequate end organ function as defined by (as per central laboratory tests):
 - Total bilirubin $\leq 1.5 \times$ ULN except for patients with Gilbert's syndrome who may only be included if total bilirubin $\leq 3.0 \times$ ULN or direct bilirubin $\leq 1.5 \times$ ULN

- Aspartate transaminase (AST) $\leq 3.0 \times \text{ULN}$
 - Alanine transaminase (ALT) $\leq 3.0 \times \text{ULN}$
 - Serum lipase $\leq 1.5 \times \text{ULN}$. For serum lipase $> \text{ULN} - \leq 1.5 \times \text{ULN}$, value must be considered not clinically significant and not associated with risk factors for acute pancreatitis
 - Alkaline phosphatase $\leq 2.5 \times \text{ULN}$
 - Creatinine clearance $\geq 50 \text{ mL/min}$ as calculated using Cockcroft-Gault formula
8. Patients must avoid consumption of grapefruit, Seville oranges or products containing the juice of each during the entire study and preferably 7 days before the first dose of study medications, due to potential CYP3A4 interaction with the study medications. Orange juice is allowed.
9. Written informed consent obtained prior to any screening procedures.
- 10a. Patients must have the following electrolyte values (as per central laboratory tests) within normal limits or corrected to be within normal limits with supplements prior to first dose of study medication:
- Potassium (potassium increase of up to 6.0 mmol/L is acceptable at study entry if associated with creatinine clearance within normal limits)
 - Total calcium (corrected for serum albumin); (calcium increase of up to 12.5 mg/dl or 3.1 mmol/L is acceptable at study entry if associated with creatinine clearance within normal limits)
 - Magnesium, with the exception of magnesium increase $> \text{ULN} - 3.0 \text{ mg/dL}$; $> \text{ULN} - 1.23 \text{ mmol/L}$ associated with creatinine clearance (calculated using Cockcroft-Gault formula) within normal limits.
11. Evidence of typical BCR-ABL1 transcript [e14a2 and/or e13a2] at the time of screening which are amenable to standardized RQ-PCR quantification.

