6.3 Dose modifications

6.3.1 Dose modification and dose delay

For patients who do not tolerate the protocol-specified dosing schedule, dose interruptions and/or reductions are either recommended or mandated in order to allow the patient to continue the study treatment.

These dose modifications are summarized in [Table 6-2](#). The dose reduction indicated as “recommendations” are provided to assist investigators in the event the patient experiences toxicity. However, deviations from “mandatory” dose interruptions and/or reductions are not allowed and mandatory interruptions or reductions must be strictly followed. Re-escalation to asciminib 40 mg BID is permitted if a change in the patient’s individual benefit/risk assessment at the lower dose level is seen. Re-escalation will be allowed only once for any given patient on the asciminib arm per protocol. Permanent treatment discontinuation is mandatory for specific events indicated as such in [Table 6-2](#). Any dose changes must be recorded on the Dosage Administration Record eCRF.

A patient must discontinue treatment with either asciminib or bosutinib if, after treatment is resumed at a lower dose level, the toxicity recurs with the same or worse severity, except for recurrence of cytopenias ([Table 6-2](#)). If a patient requires a dose interruption of > 28 days for each non-hematologic toxicity, then the patient must be discontinued from the study treatment. If a hematologic toxicity (cytopenia Grade 3 or 4) lasts for more than 42 days without recovery to at least a Grade 2, despite TKI interruption and adequate management (including hematopoietic growth factors), then the patient must be discontinued from the study treatment.

Table 6-2 Criteria for dose reduction/interruption and re-initiation of asciminib and bosutinib treatment for adverse drug reactions

[figure not shown]
Dose modifications for both asciminib and bosutinib		
Please note that if a patient requires a dose interruption of > 28 days for each toxicity, then the patient must be discontinued from the study treatment		
Worst toxicity CTCAE Grade 4.03	Asciminib	Bosutinib
Investigations (Hematologic) If a hematologic toxicity (cytopenia Grade 3 or 4) lasts for more than 42 days without recovery to at least a Grade 2, despite TKI interruption and adequate management (including hematopoietic growth factors), then the patient must be discontinued from the study treatment.		
Neutropenia (ANC)		

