Grade 4 (PLT < 25 x 10 ⁹ /L)	Mandatory: Hold dose until resolved to ≤ Grade 2 (recheck CBC 2x/week), then: if resolved in ≤ 14 days, then maintain dose level if resolved in > 14 days, then reduce dose ↓ 1 dose level	Mandatory: Hold dose until resolved to ≤ Grade 2 and neutrophils ≤ Grade 2 (recheck CBC 2x/week), then: if resolved in ≤ 14 days, then maintain dose level if resolved in > 14 days, then reduce dose ↓ 1 dose level
Recurrence of all cytopenias	Recommendation: Hold dose until resolved to ≤ Grade 2, then maintain current dose level.	Recommendation: Hold dose until resolved to ≤ Grade 2, then reduce dose ↓ 1 additional level
Non-hematologic adverse reactions except where further specified in individual sections		
Grade 1	Recommendation: Maintain dose level	Recommendation: Maintain dose level
Grade 2	Recommendation: Hold dose until resolved to ≤ Grade 1, then maintain dose level	Recommendation: Maintain dose level
Grade 3	Mandatory: Hold dose until resolved to ≤ Grade 1, then reduce dose ↓ 1 dose level	Mandatory: Hold dose until resolved to ≤ Grade 1, then reduce dose ↓ 1 dose level, If clinically appropriate, re-escalation of the dose back to baseline dose level (500 mg) should be considered
Grade 4	Mandatory: Permanently discontinue patient from study drug treatment.	Mandatory: Hold dose until resolved to ≤ Grade 1, then reduce dose ↓ 1 dose level; If clinically appropriate, re-escalation of the dose back to baseline dose level (500 mg) should be considered
Investigations (Renal)		
Serum creatinine		
Grade 1 (> ULN - 1.5 x ULN)	Recommendation: Maintain dose level	Recommendation: Maintain dose level
Grade 2 (> 1.5 - 3.0 x ULN)	Recommendation: Hold dose until resolved to ≤ Grade 1 or baseline, then maintain dose level	Recommendation: Hold dose until resolved to ≤ Grade 1 or baseline, then maintain dose level
Grade 3 (> 3.0 - 6.0 x ULN)	Mandatory: Permanently discontinue patient from study drug treatment.	Mandatory: Permanently discontinue patient from study drug treatment.
Grade 4 (> 6.0 x ULN)	Mandatory: Permanently discontinue patient from study drug treatment.	Mandatory: Permanently discontinue patient from study drug treatment.

[figure not shown]
Dose modifications for both asciminib and bosutinib		
Please note that if a patient requires a dose interruption of > 28 days for each toxicity, then the patient must be discontinued from the study treatment		
Worst toxicity CTCAE Grade 4.03	Asciminib	Bosutinib
Investigations (Hepatic)		

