Isolated total Bilirubin elevation		
> ULN – 1.5 x ULN	Recommendation: Maintain dose level	Recommendation: Maintain dose level
> 1.5 - 3.0 x ULN	Recommendation: Hold dose. Monitor LFTs ^b weekly, or more frequently if clinically indicated, until resolved to ≤ 1.5 x ULN: if resolved in ≤ 14 days, then maintain dose level if resolved in > 14 days, then reduce dose ↓ 1 dose level	Recommendation: Hold dose. Monitor LFTs ^b weekly, or more frequently if clinically indicated, until resolved to ≤ 1.5 x ULN: if resolved in ≤ 14 days, then maintain dose level if resolved in > 14 days, then reduce dose ↓ 1 dose level
> 3.0 - 10.0 x ULN*	Mandatory: Hold dose. Monitor LFTs ^b weekly, or more frequently if clinically indicated, until resolved to ≤ 1.5 x ULN: if resolved in ≤ 14 days, then reduce dose ↓ 1 dose level if resolved in > 14 days, then discontinue patient from study drug treatment. The patient should be monitored weekly (including LFTs ^b), or more frequently if clinically indicated, until total bilirubin have resolved to baseline or stabilization over 4 weeks.	Mandatory: Hold dose. Monitor LFTs ^b weekly, or more frequently if clinically indicated, until resolved to ≤ 1.5 x ULN: if resolved in ≤ 14 days, then reduce dose ↓ 1 dose level if resolved in > 14 days, then discontinue patient from study drug treatment. The patient should be monitored weekly (including LFTs ^b), or more frequently if clinically indicated, until total bilirubin have resolved to baseline or stabilization over 4 weeks.
> 10.0 x ULN*	Mandatory: Permanently discontinue patient from study drug treatment. The patient should be monitored weekly (including LFTs ^b), or more frequently if clinically indicated, until total bilirubin have resolved to baseline or stabilization over 4 weeks.	Mandatory: Permanently discontinue patient from study drug treatment. The patient should be monitored weekly (including LFTs ^b), or more frequently if clinically indicated, until total bilirubin have resolved to baseline or stabilization over 4 weeks.
Isolated AST or ALT elevation		
> ULN - 3.0 x ULN	Recommendation: Maintain dose level	Recommendation: Maintain dose level

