Dose modifications for both asciminib and bosutinib		
Please note that if a patient requires a dose interruption of > 28 days for each toxicity, then the patient must be discontinued from the study treatment		
Worst toxicity CTCAE Grade 4.03	Asciminib	Bosutinib

If combined elevations of AST or ALT and total bilirubin do not meet the defined thresholds, please follow the instructions for isolated elevation of total bilirubin and isolated elevation of AST/ALT, and take a conservative action based on the degree of the elevations (e.g. discontinue treatment at the situation when hold dose is needed for one parameter and discontinue treatment is required for another parameter). After all elevations resolve to the defined thresholds that allow treatment re-initiation, re-start the treatment either at the same dose or at one dose lower if meeting a criterion for dose reduction
 
^d “Cholestasis” defined as ALP elevation (>2.0 x ULN and R value <2) in patients without bone metastasis, or elevation of ALP liver fraction in patients with bone metastasis
 
Note: The R value is calculated by dividing the ALT by the ALP, using multiples of the ULN for both values. It denotes whether the relative pattern of ALT and/or ALP elevation is due to cholestatic (R ≤ 2), hepatocellular (R ≥ 5), or mixed (R >2 and < 5) liver injury
 
* Note: If total bilirubin > 3.0 x ULN is due to the indirect (non-conjugated) component only, and hemolysis as the etiology has been ruled out as per institutional guidelines (e.g., review of peripheral blood smear and haptoglobin determination), then ↓ 1 dose level and continue treatment at the discretion of the investigator.
 
** Note: A CT scan or other imaging study to assess the pancreas, liver, and gallbladder must be performed within 1 week of the first occurrence of any ≥ Grade 3 of amylase and/or lipase. If asymptomatic Grade 2 elevations of lipase and/or amylase occur again at the reduced dose, patients will be discontinued permanently from study treatment.
 
*** Note: antidiarrheal medication is recommended at the first sign of abdominal cramping, loose stools or overt diarrhea
		

[figure not shown]

Table 6-3 Dose reduction steps for asciminib and bosutinib

Dose reduction*			
	Starting dose level – 0	Dose level – 1	
Asciminib BID	40 mg tablet BID (total daily dose 80 mg)	20 mg tablet BID (total daily dose 40 mg)	
*Dose reduction should be based on the worst toxicity demonstrated at the last dose.			

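### Table 6-2 recommends holding either drug at bilirubin levels that criterion 7 accepts in Gilbert's syndrome, with no restart at baseline

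*Combined protocol and SAP*

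**What the plan says.** **Entry.** Criterion 7 in Section 5.2, repeated with the same limits in the protocol summary, requires total bilirubin of at most 1.5 x ULN. The exception is for patients with Gilbert's syndrome, "who may only be included if total bilirubin $\leq 3.0 \times$ ULN or direct bilirubin $\leq 1.5 \times$ ULN".

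**On treatment.** Table 6-2 in Section 6.3.1 has rows for isolated total bilirubin elevation. For values above 1.5 and up to 3.0 x ULN, both drug columns carry the same recommendation: hold the dose and monitor liver tests "weekly, or more frequently if clinically indicated, until resolved to ≤ 1.5 x ULN". The dose is then kept if this took 14 days or less, and reduced one level if it took longer. Above 3.0 x ULN the hold is mandatory. A note attached to the rows above 3.0 x ULN applies "If total bilirubin > 3.0 x ULN is due to the indirect (non-conjugated) component only", with hemolysis ruled out; the instruction is "then ↓ 1 dose level and continue treatment at the discretion of the investigator".

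**Status of the row.** Table 6-2 is titled as criteria for dose reduction, interruption and "re-initiation of asciminib and bosutinib treatment for adverse drug reactions". Section 6.3.1 says that its recommendations "are provided to assist investigators in the event the patient experiences toxicity" and allows no deviation only from mandatory actions.

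**Prolonged holds.** Section 6.3.1 also states: "If a patient requires a dose interruption of > 28 days for each non-hematologic toxicity, then the patient must be discontinued from the study treatment".

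**Other rows.** Grade 2 creatinine reads "Hold dose until resolved to ≤ Grade 1 or baseline, then maintain dose level", and the Grade 3 amylase/lipase row likewise accepts a return to baseline.

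**The concern.** The bilirubin band that criterion 7 opens for Gilbert's syndrome under its total-bilirubin limb is the band in which Table 6-2 recommends a hold. A patient admitted with a known, stable value in that band meets the trigger on the entry value, and returning to that value does not satisfy the restart limit.

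What is at stake is consistent management of individual patients. One site may continue such a patient and another may hold and eventually stop study treatment on the same unchanged value. These patients have already received at least two TKIs, and the protocol itself describes their remaining options as limited.

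**Working it through.** The plan states no figure on this point. The check compares thresholds, then sizes the consequence for one patient.

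**1. Threshold comparison (Gilbert's patient, stable baseline)**

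| Baseline total bilirubin (x ULN) | Eligible | In the > 1.5–3.0 hold row | Restart limit (≤ 1.5) met at baseline | Indirect-bilirubin note (> 3.0) applies |
|---|---|---|---|---|
| 1.4 | yes | no | yes | no |
| 1.6 | yes | yes | no | no |
| 2.0 | yes | yes | no | no |
| 2.5 | yes | yes | no | no |
| 3.0 | yes | yes | no | no |

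Every admitted value above 1.5 and up to 3.0 x ULN falls in the hold row, fails the restart limit at baseline, and lies outside the note.

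**2. Above 3.0 x ULN.** The two limbs of the Gilbert's exception are joined by *or*. Read literally, a patient with direct bilirubin at or below 1.5 x ULN may enter with total bilirubin above 3.0 x ULN. There the hold is mandatory, and the note lets the patient continue only one dose level lower, although nothing has changed since entry.

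**3. Is the missing baseline alternative a pattern?** No. Creatinine and amylase/lipase accept a return to baseline. The combined AST/ALT and bilirubin row separates normal from raised baselines. So do the liver-injury criteria in Section 6.3.3.1, which refer to a multiple of baseline total bilirubin. The absence in the isolated bilirubin row looks like an omission.

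**4. Time course if a site follows the row.** Chemistry is drawn at Week 1 Day 1 and Week 2 Day 1 (Table 7-5). Take a hold prompted by the Week 2 Day 1 sample:
- Week 2 Day 1 = day 8; last dose assumed on day 8.
- 28 days without drug = days 9 to 36 (8 + 28 = 36).
- The interruption exceeds 28 days on day 37, and discontinuation is then required.
- The treatment period runs to at least 96 x 7 = 672 days.

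**5. Effect on the primary endpoint.** Section 10.4.3 counts discontinuation before Week 24 as non-response. With the planned rates and arm sizes in Section 10.8, one such stop changes the expected MMR rate by:
- asciminib: 0.35 / 148 = 0.0024, or 0.24 points;
- bosutinib: 0.15 / 74 = 0.0020, or 0.20 points.

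If that one patient would certainly have responded, the upper limits are 1/148 = 0.68 points and 1/74 = 1.35 points.

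**6. What a change can still reach.** Recruitment closed on 22-Oct-2019, and the current amendment is dated 05-Aug-2020. Assuming first dose at about randomization for the last patient:
- Week 24: 22-Oct-2019 + 168 days = 07-Apr-2020, which is 120 days before the amendment.
- Elapsed at the amendment: 168 + 120 = 288 days, about week 41.
- Chemistry visits already due on study: Week 1 Day 1, Week 2 Day 1, and Weeks 4, 8, 12, 16, 20, 24, 28, 32, 36 and 40, a total of 12.
- Left of the 96-week period: 672 − 288 = 384 days.

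**The case against.** The strongest reply is that nothing in the text compels loss of treatment. The row is a recommendation, offered for use when a patient has a toxicity, in a table titled for adverse drug reactions. Section 8.1.1 defines an adverse event as something new or worsened after consent and sends conditions already present to medical history. A stable Gilbert's value is neither new nor worse. Applying the threshold to it would put the patient on hold at the Week 1 Day 1 sample and cancel an exception that criterion 7 makes deliberately. No document reports that any site did this. All of this stands, and it keeps the point minor. It does not remove the point: the row is triggered by a laboratory value, nothing exempts a stable entry value, and an investigator who follows the recommendation reaches a mandatory stop.

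A reader might infer from Section 8.1.2.1 that the value becomes an adverse event by definition, so that the table must apply. The documents do not support that. The sentence covers dose holds that the protocol requires, and it governs adverse event reporting, not dosing. A recommended hold is not a required one.

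A reader might also expect the correction to help many patients still on treatment. It would not. By August 2020 even the last-randomized patient had about 12 chemistry visits behind them, so a Gilbert's patient still on drug with a stable raised value has in all likelihood been continued through those checks. Bosutinib patients who switch have been managed under identical row text. The remaining benefit is mainly for values that later drift across 1.5 x ULN.

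**Conclusion.** The two provisions conflict as written. Criterion 7 admits Gilbert's patients at total bilirubin above 1.5 and up to 3.0 x ULN, and the advisory row for the same band recommends holding either drug to a limit that a stable patient cannot be expected to reach. Following the recommendation literally ends in mandatory discontinuation at about day 37 in the worked case.

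The protocol does not force these patients off treatment, and the text gives no ground for claiming bias in the comparison. The row is the same in both arms, and the expected effect of one stop is 0.20 to 0.24 points on an arm's MMR rate, which is negligible. The last patient's Week 24 had also passed before the current amendment.

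This rests on three assumptions: the patient's bilirubin stays at its entry value, first dose was at about randomization, and the planned arm sizes apply (233 patients were randomized against 222 planned, and the documents give no split by arm). The documents do not give the frequency of Gilbert's syndrome, so no number of affected patients is claimed. The point is a minor patient-management and consistency correction.

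**What to change.** Make two edits to Table 6-2:

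1. In the isolated total bilirubin row for > 1.5–3.0 x ULN, both columns, change the restart limit to *≤ 1.5 x ULN or baseline*. Criterion 7 holds all other patients to 1.5 x ULN at entry, so with baseline read as the entry value this changes nothing for them.
2. Add a footnote that a stable, indirect-only entry value in a patient with Gilbert's syndrome is not by itself a trigger for a hold or dose reduction, including above 3.0 x ULN if the patient entered under the direct-bilirubin limb.

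The footnote removes the trigger on an unchanged value; the restart wording deals with a genuine rise that settles back. The footnote should also say that baseline means the study-entry value, so that a rise acquired on bosutinib does not become the reference after a switch. The restart limit in the mandatory > 3.0–10.0 x ULN row can stay as it is, and the combined-elevation rule is untouched.

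No new procedures, data or analyses are needed. Section 12.1 requires a written amendment with ethics approval and, where applicable, Health Authority approval. That effort is not justified for this alone, so the edits can go into the next amendment.

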5.3 Exclusion criteria

Patients eligible for this study must not meet **any** of the following criteria:

1. Known presence of the T315I or V299L mutation at any time prior to study entry
2. Known second chronic phase of CML after previous progression to AP/BC
3. Previous treatment with a hematopoietic stem-cell transplantation
4. Patient planning to undergo allogeneic hematopoietic stem cell transplantation
5. Cardiac or cardiac repolarization abnormality, including any of the following:
 - History within 6 months prior to starting study treatment of myocardial infarction (MI), angina pectoris, coronary artery bypass graft (CABG)
 - Clinically significant cardiac arrhythmias (e.g., ventricular tachycardia), complete left bundle branch block, high-grade AV block (e.g., bifascicular block, Mobitz type II and third degree AV block)
 - QTcF at screening $\geq 450 \text{ msec}$ (male patients), $\geq 460 \text{ msec}$ (female patients)
 - Long QT syndrome, family history of idiopathic sudden death or congenital long QT syndrome, or any of the following:

- Risk factors for Torsades de Pointes (TdP) including uncorrected hypokalemia or hypomagnesemia, history of cardiac failure, or history of clinically significant/symptomatic bradycardia
 - Concomitant medication(s) with a “Known risk of Torsades de Pointes” per www.crediblemeds.org/ that cannot be discontinued or replaced 7 days prior to starting study drug by safe alternative medication.
 - Inability to determine the QTcF interval
6. Severe and/or uncontrolled concurrent medical disease that in the opinion of the investigator could cause unacceptable safety risks or compromise compliance with the protocol (e.g. uncontrolled diabetes, active or uncontrolled infection, pulmonary hypertension)
 7. History of acute pancreatitis within 1 year of study entry or past medical history of chronic pancreatitis
 9. History of acute or chronic liver disease
 10. Known presence of significant congenital or acquired bleeding disorder unrelated to cancer
 11. History of other active malignancy within 3 years prior to study entry with the exception of previous or concomitant basal cell skin cancer and previous carcinoma in situ treated curatively
 12. Known history of Human Immunodeficiency Virus (HIV), chronic Hepatitis B (HBV), or chronic Hepatitis C (HCV) infection. Testing for Hepatitis B surface antigen (HBs Ag) and Hepatitis B core antibody (HBcAb / anti HBc) will be performed at screening
 13. Impairment of gastrointestinal (GI) function or GI disease that may significantly alter the absorption of study drug (e.g. ulcerative disease, uncontrolled nausea, vomiting, diarrhea, malabsorption syndrome, small bowel resection, or gastric bypass surgery)
 - 14a. Treatment with medications that meet one of the following criteria and that cannot be discontinued at least one week prior to the start of treatment with study treatment
 - Moderate or strong inducers of CYP3A
 - Moderate or strong inhibitors of CYP3A
 15. Previous treatment with or known/ suspected hypersensitivity to asciminib or any of its excipients.
 16. Previous treatment with or known/ suspected hypersensitivity to bosutinib or any of its excipients.
 17. Participation in a prior investigational study within 30 days prior to randomization or within 5 half-lives of the investigational product, whichever is longer
 18. Pregnant or nursing (lactating) women
 - 19a. Women of child-bearing potential, defined as all women physiologically capable of becoming pregnant, unless they are using highly effective methods of contraception during dosing and for 3 days after last dose of asciminib and one month after last dose of bosutinib. Highly effective contraception methods include:

- Total abstinence (when this is in line with the preferred and usual lifestyle of the subject. Periodic abstinence (e.g., calendar, ovulation, symptothermal, post-ovulation methods) and withdrawal are not acceptable methods of contraception)
- Female sterilization (have had surgical bilateral oophorectomy (with or without hysterectomy) total hysterectomy or bilateral tubal ligation at least six weeks before taking study treatment). In case of oophorectomy alone, only when the reproductive status of the woman has been confirmed by follow up hormone level assessment
- Male sterilization (at least 6 months prior to screening). The vasectomized male partner should be the sole partner for that subject.
- Use of oral, injected or implanted hormonal methods of contraception or placement of an intrauterine device (IUD) or intrauterine system (IUS) or other forms of hormonal contraception that have comparable efficacy (failure rate <1%), for example hormone vaginal ring or transdermal hormone contraception.
- In case of use of oral contraception women should have been stable on the same pill for a minimum of 3 months before taking study treatment.
- Women are considered post-menopausal and not of child bearing potential if they have had 12 months of natural (spontaneous) amenorrhea with an appropriate clinical profile (e.g. age appropriate, history of vasomotor symptoms) or have had surgical bilateral oophorectomy (with or without hysterectomy), total hysterectomy or bilateral tubal ligation at least six weeks before taking study medication. In the case of oophorectomy alone, women are considered post-menopausal and not of child bearing potential only when the reproductive status of the woman has been confirmed by follow up hormone level assessment.

6 Treatment

